1. BACKGROUND

1.1 Study Disease

Erectile Dysfunction(ED) is a condition with an inability to develop or maintain an erection of the penis upon sexual stimulation. It occurs in association with aging, chronic illnesses and various modifiable risk factors. Amongst the modifiable risk factors, ED shares the most common risk factors with Coronary Artery Disease(CAD) which are smoking, hypertension and hyperlipidemia¹. Even though

it is not a part of normal aging, it is seen in 52% men in the age group 40 to 70 years, with a higher rate in the men more than 70 years².

Penile erections are as a result of an interaction of the normal physiologic processes involving the central and peripheral nervous system, endocrine and vascular systems. Any imbalances in these processes will lead to the development of ED.

The phases of erection are,

- Dilation of the arterioles and arteries as a result of increased blood flow.
- Trapping of incoming blood by the expanding sinusoids.
- Compression of the venous plexuses reducing venous outflow.

- Stretching of the tunica to its maximum capacity, occluding the emissary veins and decreasing the venous outflow to a minimum.
- Erections occurs

ED can be classified in to two groups, Organic and Psychogenic.

Vasculogenic ED which belongs to the Organic group, can be either due to arteriogenic, or venogenic or mixed².

Arteriogenic ED is caused due to a narrowed lumen due to increased resistance of the arteries, enhanced basal and myogenic tone leading to vasoconstriction, and endothelial dysfunction resulting in impaired endothelium dependent vasodilation.

Venogenic ED occurs mainly due to failure of adequate venous occlusion.

The inadequate venous occlusion can be due to

- Development of large venous channels draining the corpora cavernosa.
- Degenerative disease (old age, Diabetes) or penile fracture (traumatic injury to the tunica albuginea) resulting in the inadequate compression of the veins.
- Alteration in the structure of the fibroelastic components resulting in venous leak.
- Acquired venous shunts.

1.2 Study Interventions

Renova-ED is a Linear Shockwaves (LISW) device which incorporates a unique shockwave transducer operable to deliver shockwaves to a treated region confined to a narrow rectangle. Shockwaves generation follows the electromagnetic principle.

Linear Shockwaves (LISW), as a treatment for ED has been in evaluation in contemporary medicine (see section 1.4). It has been in use for the last three years.

The present study is about a device called "Renova-ED", in which shockwaves are focused onto line segments for improved organ coverage. Shockwaves produced by "Renova-ED" are aimed at the left and right corpora cavernosa and the crura. The study is aimed at determining the safety and effectiveness of this new type LISW in the relief of ED.

1.3 Rationale

LISW has been known to bolster angiogenesis by increasing the levels of vascular endothelial growth factor.

Principal mode of action used in other disease:

Coronary Artery Disease: Kikuchi et al.³ showed significantly improved symptoms and decreased nitroglycerin use in patient who had a coronary artery bypass grafting and were suffering from stable angina.

Bone Healing: Haupt et al.⁴ showed that Low intensity shock waves treated group showed radiological signs of faster healing.

Calcifying tendinitis: Rompe et al.⁵ showed that shock wave to patient suffering from calcifying tendinitis showed a 62.5% partial and complete disintegration of the the deposits. Moreover, 85% of the patients reported improvement at 24-week follow up period.

Diabetic Foot Ulcers: Wang et al.⁶ showed that Extracoproral Shock Wave Therapy (ESWT) to patients with diabetic foot ulcer showed complete improvement in 31%

and partial improvement in 58%. Moreover, ESWT showed significantly better clinical results and local blood flow perfusion, higher cell concentration, and activity than the Hyperbaric Oxygen group.

1.4 Preliminary Studies

Contemporary literature shows two important studies in this field both conducted by Vardi et al^{7,8}.

The efficacy trial study published in 2010 recruited 20 men with vasculogenic ED and were given serial 2 sessions of treatment for about 3 weeks followed by 3 – week no intervention period. At 1-month duration there was a significant improvement in their erectile function measured by International Index of Erectile Function ED (IIEF-ED) domain scores (20.9 5.8 vs 13.5 4.1, $p < 0.001$). This significant result was consistent at 6-month follow up. Moreover, no pain or adverse event was noted during the follow-up period.

The second randomized, double-blind, sham controlled study by showed that treatment group showed better outcome than control group measured using International Index of Erectile Function-Erectile Function domain (mean SEM 6.7 0.9 vs 3.0 1.4, $p 0.0322$) at the first follow-up. Additionally, penile hemodynamics improve significantly in the treatment group in comparison to control group (maximal post-ischemic penile blood flow 8.2 vs 0.1 ml per minute per dl, $p 0.0001$).

2. HYPOTHESIS

2.1 Alternate Hypothesis (H_A):

Active Treatment groups will show a >2-point increase in the IIEF-EF score from baseline for mild erectile dysfunction, and >5 points for moderate erectile dysfunction and will show significant change.

2.2 Null Hypothesis (H₀):

There is no difference from baseline and after-treatment in Treatment groups for alleviating ED measured using IIEF-EF score.

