7. STUDY DESIGN, CLINICAL, RADIOLOGICAL, LABORATORY AND SURGICAL EVALUATIONS

7.1 Study Design

This is a prospective, randomized, clinical study aimed to evaluate the safety and efficacy of the two treatment schedules on symptomatic ED patients. The patients are randomized in a 1:1 ratio into two active treatment groups. (Refer section 18)

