10.5 Statistical Analysis and Power calculation

The average and standard deviation of all relevant variables, including demographic and baseline characteristics, primary and secondary outcomes will be calculated.

IIEF-EF and EHS scores will be analyzed using ANOVA with repeated measures throughout the study, in order to compare the trends of groups A and B.

GAQ, SEP and success rates will be analyzed and compared between the groups according to Fisher's exact test in each of the endpoints. The statistical significance will be set at $P < 0.05$.

Demographic characteristics such as age and ED duration will be compared between groups A and B using student's test. Other demographic characteristics, such as medical background and risk factors will be compared between these groups using Fisher's exact test.

A sample of 80 men with failing scores on the IIEF SEP2 question will be randomized 1:1 into one of two arms (low intensity or high intensity treatment) using a permuted random block algorithm. We hypothesize that following placebo treatment between 0 and 5% of men will pass the SEP2 question and at least 35% of men treated at either intensity level will pass. We have two co-primary

endpoints, the percentage of men passing after low intensity and high intensity relative to placebo, which will be assessed by two independent Fisher’s exact tests. Each of these tests will be conducted with a 0.025 alpha error level to allow for a 0.05 experiment wide type I error rate. Power calculations done in SAS 9.4 suggest that with 40 men randomized into each group we will have at least 85% power to detect the difference between a 5% and 35% response rate. So long as our non-compliance/drop-out rate remains above 10% will will have at least 80% power (see Figure 1).

Computed N per Group			
Index	Nominal Power	Actual Power	N per Group
1	0.80	0.813	37
2	0.85	0.852	40
3	0.90	0.900	45

Figure 1. Sample size needed for 80% 85% and 90% nominal power for a Fisher’s exact test with alpha = 0.025 (using an exact conditional distribution with the Walters normal approximation method).

10.6 Randomization:

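### The mild-ED success criterion (>2 IIEF-EF points over baseline) lies below the 3.0-point sham gain the plan cites, so a sham-sized response could meet it and be read as effectiveness

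*Combined protocol and SAP*

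**What the plan says.** Section 2.1 (alternate hypothesis) states that "Active Treatment groups will show a >2-point increase in the IIEF-EF score from baseline for mild erectile dysfunction". The same sentence sets a higher bar for the more severe group and adds a significance condition: ">5 points for moderate erectile dysfunction and will show significant change". Section 2.2 sets the null within the groups: "There is no difference from baseline and after-treatment in Treatment groups". Section 1.2 names effectiveness of the device as an aim.

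Section 1.4 describes the second preliminary study as sham controlled ("The second randomized, double-blind, sham controlled study") and gives its IIEF-EF result at first follow-up, treated versus control, as "mean SEM 6.7 0.9 vs 3.0 1.4".

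In this trial there is no sham arm (7.1): "The patients are randomized in a 1:1 ratio into two active treatment groups". Section 10.5 says that "IIEF-EF and EHS scores will be analyzed using ANOVA with repeated measures throughout the study", for the stated purpose of comparing the trends of A and B. The power text in 10.5 does mention placebo, but for passing SEP2, and no placebo group is randomized.

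**The concern.** The bar for mild ED is lower than the gain that the plan itself reports under sham. Requiring a significant change as well does not separate the two, because the comparison is with baseline and the cited sham gain is also distinguishable from zero. With two active arms and an A-versus-B analysis, no other IIEF-EF result in the plan can do so. At stake is the reading of the primary endpoint: a result that satisfies 2.1 in mild ED could be presented as evidence that the device works when a response of the size seen with sham could produce it.

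**Working it through.** **Inputs from the documents.** Thresholds >2 (mild) and >5 (moderate), with significant change (2.1). Active 6.7, SEM 0.9; sham 3.0, SEM 1.4 (1.4). 40 patients per arm (10.6). Significance level 0.05 (10.5; two-sided assumed).

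**Assumptions.** The documents give no SD of change and no number of mild patients, and they do not define mild. I use SD 5.8 and 7, and n = 10, 20 and 40 mild patients. The value 5.8 is the spread printed beside a follow-up score in 1.4, not an SD of change. n = 40 would need a whole arm to be mild. n = 80 would need every patient to be mild and the arms pooled, so I do not use it here. Significance is taken as a paired t test against baseline, since 10.5 names no within-group test.

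**1. The plan's own figures.** Cited comparison: 6.7 − 3.0 = 3.7; SE = √(0.9² + 1.4²) = 1.664; t = 3.7/1.664 = 2.22; p = 0.032 on 40 df and 0.034 on 30 df. This agrees with the printed 0.0322, so the SEMs can be relied on. The only power figure (0.852 with 40 per arm, 5% versus 35%, alpha 0.025) also reproduces: 0.8515 by the Walters approximation and 0.850 by exact enumeration. It concerns SEP2 and says nothing about the IIEF-EF.

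**2. Thresholds against the sham gain.** 3.0 − 2 = 1.0, so the mild bar is 1.0 point below the sham mean. 5 − 3.0 = 2.0, so the moderate bar is 2.0 points above it.

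**3. Sham gain against zero.** z = 3.0/1.4 = 2.14, two-sided p = 0.032. (The printed 0.0322 is the between-arm p-value; the closeness is a coincidence.) 95% interval: 3.0 ± 1.96 × 1.4 = 0.26 to 5.74. The sham arm's size is not given. With t on 19 df the interval is 0.07 to 5.93; on 9 df it would be −0.17 to 6.17 and include zero.

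**4. Chance that a true gain of 3.0 meets the mild criterion.** Point condition: P(mean > 2) = Φ((3.0 − 2)/(SD/√n)). Both conditions: mean > 2 and mean/(s/√n) > t(0.975, n − 1).

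Example, SD 5.8, n = 20: SE = 5.8/√20 = 1.297; Φ(1/1.297) = 0.78. Significance needs a mean of about 2.093 × 1.297 = 2.71, so it is the binding condition, and the joint probability falls to 0.59.

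| SD | n mild | P(mean > 2) | P(mean > 2 and significant) | P(mean > 5) |
|---|---|---|---|---|
| 5.8 | 10 | 0.71 | 0.31 | 0.14 |
| 5.8 | 20 | 0.78 | 0.59 | 0.06 |
| 5.8 | 40 | 0.86 | 0.85 | 0.01 |
| 7 | 10 | 0.67 | 0.23 | 0.18 |
| 7 | 20 | 0.74 | 0.44 | 0.10 |
| 7 | 40 | 0.82 | 0.75 | 0.04 |

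For SD 4 to 8 and n = 20 to 40, the joint probability runs from 0.36 to 0.94, and P(mean > 5) from 0.001 to 0.13.

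**5. Would 3.0 serve as a pass mark?** Requiring the lower 95% limit to exceed a fixed 3.0 needs an observed mean of 3.0 + t × 5.8/√n = 5.7, 4.9 and 4.3 at n = 20, 40 and 80. Allowing for the error in the sham estimate, it is 3.0 + 1.96 × √(5.8²/n + 1.4²) = 6.7, 6.3 and 6.0. The fixed rule ignores the larger part of the uncertainty.

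**The case against.** Several arguments on the other side carry weight.

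- *The criterion has two parts.* Looking only at the mean exceeding 2 overstates the risk. This stands: with 10 mild patients the joint probability is 0.23 to 0.31, so a sham-sized response could meet the criterion but need not.
- *The populations differ.* A threshold for mild ED is set against a sham mean over all severities. Men near the upper entry limit of 25 on a 0–30 scale have little room to gain, and their sham response may be smaller. This stands as a limit. Nothing in the documents shows that it is smaller.
- *The figures are not labelled as changes.* Section 1.4 does not say so. As end scores, though, 6.7 and 3.0 would be implausible beside the 13.5 and 20.9 in the same section, so change from baseline is the natural reading.
- *The root cause is the missing sham arm, not the threshold.* Against a concurrent sham, a 2-point threshold of relevance would do no harm. That is right, and it is why the remedy concerns how the thresholds are interpreted rather than their size. It does not remove the point: within the chosen design, 2.1 is the only IIEF-EF standard of benefit.
- *No rule in 10.5 uses the thresholds.* True. That the trial will declare effectiveness on meeting 2.1 is an inference; the documents leave that reading open and do not require it.

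A reader might also infer that the >5 criterion is compromised, because 5 lies inside 0.3 to 5.7. The documents do not support that. The interval shows that the sham estimate is imprecise; a mean of 3.0 does not meet >5.

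**Conclusion.** The point holds for mild ED. The bar is 1.0 point below the cited sham gain, the significance condition is set against baseline, and no sham comparison exists, so an effectiveness conclusion drawn from 2.1 as written would be unsound. With a true gain of 3.0, both conditions are met with probability about 0.59 and 0.85 (20 and 40 mild patients, SD 5.8), 0.44 and 0.75 (SD 7), and 0.23 to 0.31 (10 patients). These figures rest on an assumed SD of change, an assumed number of mild patients, a two-sided paired test, and a sham gain that carries over to mild ED. The comparison of 2 with 3.0 needs only the reading of the cited figures as changes.

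Two stronger readings go too far. It does not follow that a sham-sized response would certainly satisfy 2.1. Nor can 3.0 be treated as the known sham effect that the device must beat: it is imprecise, covers all severities, and comes from the first follow-up only, while section 3.1 covers 1, 3 and 6 months.

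**What to change.** In 2.1 and 10.5, describe >2 and >5 as descriptive thresholds of clinical relevance. State that meeting them, even with a significant change from baseline, does not show benefit over sham.

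Report the mean IIEF-EF change with its 95% confidence interval per arm and severity stratum, with mild and moderate defined. Set it beside the cited sham gain of 3.0 (95% interval 0.3 to 5.7, first follow-up only), labelled as an uncontrolled cross-study comparison. Do not use 3.0 as a fixed pass mark.

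Sections 7.3 and 7.4 contradict each other on PDE5i use after treatment: the first has patients avoid it through follow-up, the second has them resume their baseline use after the last session. The two must be reconciled before any such comparison is interpreted.

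The cost is a few sentences, with no added patients or visits. The downside is that the trial can make only a weaker claim of effectiveness.

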3. OBJECTIVES

3.1 Primary Efficacy Objective

To evaluate change of IIEF-EF score⁹ from baseline to follow-ups 1, 3 and 6 months' post treatment (appendix I).

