6. PATIENT SELECTION/ELIGIBILITY CRITERIA

6.1 Inclusion (Eligibility) Criteria

- The patient must be able willing and able to provide informed consent.
- The patient is a male between ≥ 30 and ≤ 80 years of age.
- The patient has ED of Vasculogenic origin determined by penile duplex ultrasound.
- The patient is PDE5i responsive, meaning he is able to achieve and maintain an erection under the effect of the maximal dosage of PDE5i.
- The patient has been in a stable heterosexual relationship for over 3 months prior to enrollment.
- A minimum of 2 sexual attempts per month for at least one month prior to enrollment – as documented by the Sexual Health Questionnaire (SHIM).
- The patient is suffering from erectile dysfunction lasting for over 6 months and not more than 5 years as per history provided by patient.
- IIEF-EF score between 11 and 25.
- Testosterone level 300-1000 ng/dL within 1 month prior to enrollment.
- A1C level $\leq 7\%$ within 1 month prior to enrollment.
- Patients have at least a natural tumescence during sexual stimulation (EHS score ≥ 1).

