10. STATISTICAL CONSIDERATIONS

10.1 Primary Study Endpoints

The IIEF-EF questionnaire (appendix I) was chosen as the primary clinical efficacy assessment tool in this study. The total score (range 0-30) will be used for statistical analysis.

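### The IIEF-EF analysis is pooled over severity and makes no comparison with 2 or 5 points, so it cannot show whether the severity-specific gains in the alternate hypothesis are reached

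*Combined protocol and SAP*

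**What the plan says.** All references are to the combined protocol and SAP.

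- **2.1 (alternate hypothesis):** the active groups will show a ">2-point increase in the IIEF-EF score from baseline for mild erectile dysfunction, and >5 points for moderate erectile dysfunction", and the change will be significant.
- **2.2 (null):** "There is no difference from baseline and after-treatment in Treatment groups for alleviating ED measured using IIEF-EF score". It has no severity split and no threshold.
- **3.1 (primary objective):** "To evaluate change of IIEF-EF score" from baseline to months 1, 3 and 6, for all men together.
- **6.1 (eligibility):** one range, "IIEF-EF score between 11 and 25". Neither this section nor the IIEF-EF appendix says which scores are mild and which moderate.
- **10.1 (primary endpoint):** "The total score (range 0-30) will be used for statistical analysis".
- **10.5 (analysis):** "IIEF-EF and EHS scores will be analyzed using ANOVA with repeated measures throughout the study". The stated purpose is a contrast between the arms: "in order to compare the trends of groups A and B". It gives no severity factor, subgroup, or test against 2 or 5 points. It adds that "GAQ, SEP and success rates will be analyzed and compared between the groups" by Fisher's exact test, but does not define success.
- **10.5 and 10.6 (randomisation):** permuted blocks, 1:1, 40 men per arm, with no severity stratum.

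**The concern.** IIEF-EF is the primary efficacy measure, and 2.1 makes its hypothesis depend on severity. The analysis then drops severity. Followed exactly, 10.5 produces a comparison of the two schedules' trends and, at most, a mean change over time for each arm across all severities. Neither shows whether mild men gained more than 2 points or moderate men more than 5.

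Three things are left open when the results come in: which baseline scores count as mild, what counts as success, and which of the three visits decides. The classification matters for individual men. Someone who gains 4 points is above one threshold and below the other, so his result depends on a cut-point the plan does not state.

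**Working it through.** **1. The plan's own figures.** The only computed figures are the sample sizes in 10.5 for SEP2 pass rates of 5% and 35% at alpha 0.025. With the Walters arcsine approximation, two-sided:

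power = Φ( √(2n) × [asin√(p2 − 1/(2n)) − asin√(p1 + 1/(2n))] − z(1−α/2) )

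This gives 0.813 at n = 37, 0.852 at n = 40 and 0.900 at n = 45, matching the plan's table. No IIEF-EF gain, SD or severity mix enters the formula, so the sample size gives no assurance about the thresholds in 2.1.

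**2. What a mean over severities can show.** Let w be the share of men with moderate ED. The documents do not give it, so 0.3 to 0.7 is assumed.

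mean gain in an arm = w × moderate gain + (1 − w) × mild gain

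With gains exactly at the thresholds:

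| w | Mean gain |
|---|---|
| 0.3 | 0.3 × 5 + 0.7 × 2 = 2.9 |
| 0.5 | 0.5 × 5 + 0.5 × 2 = 3.5 |
| 0.7 | 0.7 × 5 + 0.3 × 2 = 4.1 |

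A mean at or below the tabulated value would be incompatible with both thresholds being exceeded. A mean above it settles nothing. The benchmark itself needs w, and so needs the missing classification.

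Take a mean gain of 4.5 within one arm at w = 0.5:

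| Mild gain | Moderate gain | Mean | Hypothesis in 2.1 |
|---|---|---|---|
| 3 | 6 | 0.5 × 3 + 0.5 × 6 = 4.5 | met |
| 6 | 3 | 0.5 × 6 + 0.5 × 3 = 4.5 | not met (moderate fails) |
| 1 | 8 | 0.5 × 1 + 0.5 × 8 = 4.5 | not met (mild fails) |

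An analysis pooled over severity returns the same mean in all three cases.

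**3. What a by-severity estimate could deliver.** The documents give no SD of change. The pilot cited in 1.4 has IIEF-EF spreads of 5.8 after and 4.1 before treatment (read as SDs), so an SD of change of 4 to 7 is assumed. For 80% power at one-sided 0.025, the true mean gain must exceed its threshold by

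(1.96 + 0.8416) × SD / √n

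- About 20 men per severity-by-arm cell (40 per arm, 50:50 mix): 2.8016 × 4/√20 = 2.5 and 2.8016 × 7/√20 = 4.4 points. The 95% CI half-width is 1.96 × SD/√20, or 1.75 to 3.07 points.
- 40 men per severity, arms combined: 1.8 to 3.1 points.

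**The case against.** The best defence is that the ANOVA keeps A and B separate and its time effect can test change from baseline. That covers the null in 2.2 and the part of 2.1 that calls for a significant change. This stands: the gap concerns the two thresholds, not the whole hypothesis. However, 10.5 declares A versus B as the purpose of the model, and a test against zero says nothing about 2 or 5 points.

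A second defence is that the success rates in 10.5 may be meant as a severity-specific responder analysis. The text does not define success or link it to 2.1. Even if it did, comparing success between A and B would not test a gain within each group, which is how 2.1 is worded.

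Three stronger readings might be inferred, and the documents do not support them.

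- **That the hypothesis could be declared met or not met at will.** The values 2 and 5 are fixed in advance, and 2.1 attaches neither to a pooled mean. A pooled result is uninformative about them and supports no claim either way. What is open is the classification, the visit and the meaning of success. That these would be settled after seeing the data is conjecture.
- **That unequal severity between the arms would create a false schedule effect.** With 40 of 80 men moderate, a split of 24/16 against 16/24 or worse occurs in about 12% of allocations. At that split, the 3-point gap between the thresholds shifts A−B by (0.6 − 0.4) × 3 = 0.6 points. The standard error is SD × √(2/40), or 0.9 to 1.6 points for an SD of 4 to 7, so the shift is 0.4 to 0.7 standard errors. This is ordinary chance imbalance, already covered by the type I error of the test.
- **That randomisation must be stratified by severity.** Section 7.3 randomises before the washout, when the post-washout baseline does not yet exist, while 10.6 opens the envelope when the man is ready for treatment. Envelopes stratified on that baseline do not fit 7.3, and the point does not need them.

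**Conclusion.** The point holds in a limited form. The alternate hypothesis for the primary measure sets two severity-specific gains, and the planned IIEF-EF analysis is pooled over severity with no comparison against either. It can address the simple null of no change but not the thresholds. This is an analysis that does not answer its own hypothesis, not only a missing detail, and it should be corrected.

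The structural conclusion rests on the text alone. The 4.5-point example assumes a 50:50 severity mix. The precision figures assume that mix and an SD of change of 4 to 7. The case does not rest on bias in the A-versus-B comparison.

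**What to change.** 1. **Classification (2.1 and 10.5).** State in advance how the post-washout baseline IIEF-EF is classed as mild or moderate. Eligibility is judged on the screening score (7.2) and baseline is measured again after washout (7.3), so the rule must cover every score that can occur, including those outside 11 to 25.
2. **Estimates (10.5).** Report mean change from baseline with 95% CI by severity within each arm at months 1, 3 and 6, set against 2 and 5 points.
3. **Visit.** Name in advance the visit or visits on which the alternate hypothesis is judged. The documents list months 1, 3 and 6 equally and give no basis for preferring one, so the sponsor must choose.
4. **Model.** Include baseline severity as a term in the repeated-measures ANOVA.
5. **Success.** Define it as a gain above the man's severity-specific threshold, and keep the planned Fisher's exact test as a supportive comparison of A with B.

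The cost is a few lines in 2.1 and 10.5, with no extra men, visits or change to randomisation. The real downside is precision: a true gain less than about 2.5 to 4.4 points above its threshold would often give an inconclusive result. The by-severity results should therefore be presented as estimates with intervals. If the sponsor does not want to judge the trial on these thresholds, 2.1 should be reworded to match the analysis.

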80 patients will be randomized 1:1 to treatment groups with 40 patients each. An online based randomization tool called randomized.org will be used. This will be prepared beforehand, with treatment option printed on the paper and then sealed in an envelope (80 envelopes). Each would have Patients ID number printed out side and randomization information inside. This would be opened after a patient has signed the informed consent and is ready to receive treatment. The PI nor the study coordinator will not have the knowledge of patient’s treatment group beforehand.

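### Section 10.5 bases its two co-primary SEP2 tests and its only power figure on a placebo group the trial does not have, which leaves the null hypothesis testable only as uncontrolled change in two active arms

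*Combined protocol and SAP*

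**What the plan says.** **Hypotheses and aim.** The null hypothesis in 2.2 reads "There is no difference from baseline and after-treatment in Treatment groups for alleviating ED measured using IIEF-EF score". Under 2.1 the active groups "will show a >2-point increase in the IIEF-EF score from baseline for mild erectile dysfunction, and >5 points for moderate erectile dysfunction". Objective 3.1 is the change in IIEF-EF "from baseline to follow-ups 1, 3 and 6" months after treatment, and 10.1 makes IIEF-EF the primary assessment tool. Section 1.2 states: "The study is aimed at determining the safety and effectiveness of this new type LISW in the relief of ED".

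**Design.** Section 7.1: "The patients are randomized in a 1:1 ratio into two active treatment groups". Section 10.6: "80 patients will be randomized 1:1 to treatment groups with 40 patients each". No placebo or sham arm is described.

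**Analysis.** In 10.5, IIEF-EF and EHS are to be "analyzed using ANOVA with repeated measures throughout the study, in order to compare the trends of groups A and B". In addition, "GAQ, SEP and success rates will be analyzed and compared between the groups" by Fisher's exact test.

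**Power.** The last paragraph of 10.5 takes men who fail SEP2, randomises them to low or high intensity, and declares two co-primary endpoints, each a SEP2 pass rate set against placebo. Each is a Fisher test at 0.025. The assumed rates are 0 to 5% on placebo and at least 35% on treatment. Figure 1 gives 37, 40 and 45 men per group, with actual power 0.813, 0.852 and 0.900.

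**PDE5i.** Section 6.1 requires PDE5i-responsive men. Section 7.3 puts the baseline questionnaires after a four-week washout and has men avoid PDE5i through treatment and follow-up. Section 7.4 has each man return to his baseline PDE5i use after the last session.

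**The concern.** The co-primary tests need placebo data that no arm supplies, so the plan's formal success criteria cannot be evaluated, and N=80 is justified by a comparison that will not be made.

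Without a control, the null hypothesis can only be examined as change from baseline under active treatment. Rejecting it would not show that the device caused the change, yet the stated aim is effectiveness. If PDE5i is resumed, an off-drug baseline is also compared with an on-drug follow-up in men selected as drug-responsive, so the drug alone could produce a rejection.

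The comparison that randomisation does protect, A against B, has no stated power or precision.

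**Working it through.** **1. Reproduce Figure 1.** Inputs from 10.5: p1 = 0.05, p2 = 0.35, alpha = 0.025, Walters approximation. Sidedness is not stated; two-sided matches.

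Power = Φ( √(2n) · [asin√(p2 − 1/(2n)) − asin√(p1 + 1/(2n))] − z(0.9875) ).

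At n = 40: √80 × (asin√0.3375 − asin√0.0625) − 2.2414 = 8.944 × (0.6199 − 0.2527) − 2.2414 = 1.043, and Φ(1.043) = 0.852. At n = 37 and 45 the formula gives 0.813 and 0.900. Full enumeration of Fisher's test at 40 per group gives 0.850. The calculation is correct for the comparison it describes.

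**2. Count the arms.** Each test needs 40 treated and 40 placebo men. Two active arms and one placebo arm would be 3 × 40 = 120. The plan has 40 + 40 = 80, all active, so there are no placebo men.

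**3. Set the power paragraph beside the rest of the plan.**

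| Point | Power paragraph, 10.5 | Elsewhere |
|---|---|---|
| Primary endpoint | SEP2, co-primary | IIEF-EF primary (3.1, 10.1); SEP2 secondary (3.2, 10.2) |
| Arms | Low and high intensity | Two schedules with equal total shocks per region: 5 × 720 = 6 × 600 = 3,600 (7.4) |
| Population | Failing SEP2 | Not an entry criterion (6.1) |
| Comparator | Placebo | None (7.1, 7.4, 10.6) |
| Drop-out | At least 80% power if the rate stays above 10% | Reads as a slip for below: 36 per group gives 0.799 (Walters) or 0.821 (enumeration) |

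**4. What A against B can deliver on IIEF-EF.** The documents give no SD of change, so 5 to 9 is assumed. Two rough checks use 1.4:
- Reading the pilot's 5.8 and 4.1 as SDs, √(5.8² + 4.1² − 2r·5.8·4.1) = 7.1, 6.0 and 5.2 for r = 0, 0.3 and 0.5.
- The SEM of 1.4 in the cited sham arm implies 1.4√m = 6.3, 7.7 and 8.9 for an assumed m = 20, 30 and 40 men.

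The unadjusted 95% CI half-width is t(0.975, 2n − 2) × SD × √(2/n). For n = 40 and SD 5 this is 1.991 × 5 × 0.2236 = 2.23. Power and detectable difference use the noncentral t, two-sided 0.05.

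| SD | 5 | 6 | 7 | 8 | 9 |
|---|---|---|---|---|---|
| Half-width, 40 per arm | 2.23 | 2.67 | 3.12 | 3.56 | 4.01 |
| Half-width, 36 per arm | 2.35 | 2.82 | 3.29 | 3.76 | 4.23 |
| Detectable at 80% power, 40 per arm | 3.17 | 3.81 | 4.44 | 5.07 | 5.71 |
| Detectable at 80% power, 36 per arm | 3.35 | 4.02 | 4.69 | 5.36 | 6.03 |
| Power for 2 points, 40 per arm | 42% | 31% | 24% | 20% | 17% |

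**5. What A against B can deliver on SEP2.** Fisher enumeration, 40 per arm, two-sided 0.05: 35% against 55, 60, 65 and 70% has power 37, 55, 72 and 86%. If both arms pass at 35%, which the plan's assumption allows, the rejection probability is 2.8%.

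**The case against.** The best defence is that this is a schedule-comparison trial. Section 7.1 aims to evaluate two schedules, two active arms can do that, and no passage claims superiority to sham on IIEF-EF. That defence stands as far as it goes. It does not rescue the power paragraph, which declares placebo comparisons as co-primary, and it does not fit the aim in 1.2 or the within-arm hypotheses in section 2.

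A second defence is that repeated-measures ANOVA already yields a time effect. That is right. The null hypothesis is not untestable; the unnamed contrast and the undefined success rates are mostly missing detail and are not the main fault here.

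Three stronger readings are tempting, and the documents do not support them:
- **The 85% is miscalculated.** It reproduces; it belongs to another design.
- **The plan will declare efficacy on rejecting the null hypothesis alone.** It does not say so, and 2.1 adds the 2- and 5-point thresholds, although 10.5 specifies no test of them.
- **One can calculate how often an inert device would succeed, from the 3.0 cited for sham in 1.4.** Section 1.4 does not say that 3.0 is a change from baseline, and no SD of change is given. The chance of meeting 2.1 would turn on what non-device change is assumed in mild and in moderate men, and on the unresolved PDE5i rule. No such figure is relied on here.

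**Conclusion.** Wrong as written. Neither co-primary test can be run, and the 85% power does not apply to this trial. This follows from the allocation alone and needs no assumption.

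As a consequence, the null hypothesis addresses only uncontrolled change within active arms, and the contradiction between 7.3 and 7.4 leaves open whether that change includes a drug effect.

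The size of what remains depends on the assumed SD of 5 to 9. A against B would be estimated to within 2.2 to 4.0 points with 40 per arm, or 2.4 to 4.2 with 36. The difference detectable with 80% power is 3.2 to 5.7 points, or 3.4 to 6.0 with 36. These figures are unadjusted; baseline adjustment may narrow them by an amount the documents do not allow one to state.

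**What to change.** 1. **In 10.5**, delete the placebo co-primary tests, the 5% against 35% power statement, Figure 1, the intensity labels, the SEP2-failure wording and the drop-out sentence. Keep SEP2 as a secondary A-against-B Fisher comparison.
2. **State that N=80 was not derived for A against B**, and report what it delivers: the half-widths and detectable differences above with their SD assumption, and 72% power for SEP2 at 35% against 65%.
3. **Name one primary comparison on IIEF-EF.** State that A against B is the only randomised comparison, adjust it for the post-washout baseline, give a 95% CI, and state that non-significance is not equivalence. Report within-arm change from that baseline at months 1, 3 and 6 with 95% CIs, labelled descriptive and uncontrolled. If within-arm change is tested instead, split alpha over the two arms: two independent tests at 0.05 would give 1 − 0.95² = 9.75% family-wise error.
4. **In 1.2 and 2**, state that within-arm change does not by itself support an efficacy claim.
5. **Reconcile 7.3 and 7.4** on PDE5i during follow-up, and record actual use at each planned visit.

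The cost is text changes and one recorded item at existing visits, with no extra patients or visits. The downside is a narrower claim: within-arm description plus a schedule comparison with only 42% to 17% power for a 2-point difference (40 per arm, SD 5 to 9). An efficacy claim would need a concurrent sham arm, which at 40 per arm means 120 men and is a different trial.
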